6.2 PARTICIPANT DISCONTINUATION/WITHDRAWAL FROM THE STUDY

See above 7.1

Participants are free to withdraw from participation in the study at any time upon request. An investigator may discontinue or withdraw a participant from the study for the following reasons:

- a) In the opinion of the Investigator, the participant's health or safety would be compromised by continuing in the study
- b) In the opinion of the Investigator, it is in the participant's best interest to discontinue participation in the study
- c) During the study, (female) participant becomes pregnant

Significant study intervention non-compliance

- If any clinical adverse event (AE), laboratory abnormality, or other medical condition or situation occurs such that continued participation in the study would not be in the best interest of the participant
- If the participant meets an exclusion criterion (either newly developed or not previously recognized) that precludes further study participation
- Participant unable to receive study intervention for 2 consecutive visits
- CGM usage < 70% of sensor period

The reason for participant discontinuation or withdrawal from the study will be recorded on the Case Report Form (CRF). Subjects who sign the informed consent form and are randomized but do not receive the study intervention may be replaced. Subjects who sign the informed consent form, and are randomized and receive the study intervention, and subsequently withdraw, or are withdrawn or discontinued from the study, will not be replaced.

6.3 LOST TO FOLLOW-UP

A participant will be considered lost to follow-up if he or she fails to return for 2 consecutive scheduled visits and is unable to be contacted by the study site staff.

The following actions must be taken if a participant fails to return to the clinic for a required study visit:

- The site will attempt to contact the participant and reschedule the missed visit within 7 days and counsel the participant on the importance of maintaining the assigned visit schedule and ascertain if the participant wishes to and/or should continue in the study.
- Before a participant is deemed lost to follow-up, the investigator or designee will make every effort to regain contact with the participant (where possible, 3 telephone calls and, if necessary, a certified letter to the participant's last known mailing address or local equivalent methods). These contact attempts should be documented in the participant's medical record or study file.
- Should the participant continue to be unreachable, he or she will be considered to have withdrawn from the study with a primary reason of lost to follow-up.

7 STUDY ASSESSMENTS AND PROCEDURES

7.1 EFFICACY ASSESSMENTS

Aim 1a

Primary Outcome: Mean daily glucose, as measured by CGM and POC BG

Secondary Outcomes: Incidence of hypoglycemia by POC BG and CGM (< 70 mg/dl), glycemic variability [% coefficient of variability (%CV), mean amplitude of glucose excursions (MAGE)], rates of asymptomatic, and nocturnal CGM-detected hypoglycemia (<70 mg/dl, < 54 mg/dl and equal to 40 mg/dl), % time in hypoglycemia (< 70 mg/dl, < 54 mg/dL), time (%) in target range (70-180 mg/dl) and time (%) in hyperglycemia (>180 mg/dL, >250 mg/dl), 10-90% glucose percentiles, and mean hourly interstitial glucose before, during and after dialysis.

After obtaining informed consent (Aim 1a), we will collect from the electronic medical records the following information: Demographics (age, sex, ethnicity, height, weight, BMI, employment, educational level) medical history (length of diabetes, current medications, prior anti-diabetic medications, cause of renal disease, co-morbidities, smoking and surgical history), physical exam findings during study visits (blood pressure, height, weight), and characteristics included in the inclusion/exclusion criteria, following HIPAA rules. We will also collect available laboratory data (hemoglobin, hematocrit, hemoglobin A1c, creatinine, urea, uric acid, phosphorus, PTH, vitamin D, lipid panel).

Subjects will complete a food record for three (3) days for caloric intake analysis, one (1) on a pre-dialysis day, one (1) on dialysis day and one (1) after a dialysis day⁶⁵, with instructions provided by the study coordinators.

Aim 1b. In Aim 1b, we will perform accuracy comparisons (see below) between matched glucose pairs obtained by the CGM vs POC (standard of care, as available).

Primary Outcome: Mean absolute relative difference (%MARD, calculated as the average relative difference between CGM, POC BG and intra-dialysis YSI matched glucose pairs).

Secondary Outcomes: %MARD for glucose <70 mg/dL, <54 mg/dL, 70-180 mg/dL, >180 mg/dL, >250 mg/dL, % MARD during non-dialysis and during dialysis hours. Proportion of CGM values within $\pm 20\%$ or ± 20 mg/dL (%20/20) of reference glucose values <70 mg/dL, <100 mg/dL, >100 mg/dL and >250 mg/dL, and the analogous %15/15, %30/30. We will utilize the Clarke Error Grid (CEG) and Surveillance Error Grid (SEG) analysis to evaluate for clinical risk of CGM errors⁶⁸.

Dataset for analysis: Each venous or POC BG value (as available) will be paired with the following CGM value within 5 min; these matched pairs will form the analysis data set. YSI/POC matched pairs within the CGM reportable range of 40–400 mg/dL will be evaluated.

Aim 2.

Primary Outcomes: Differences in mean percentage time-in-hypoglycemia (< 70 mg/dL) during the intervention phase, compared to control in both groups (i.e. intervention-control vs. control-intervention).

Secondary Outcomes: CGM-measured % time-in-range (70-180 mg/dL), % time in hypoglycemia (<54 mg/dL), % time in hyperglycemia (>180 mg/dL, >250 mg/dL), % coefficient of variation (%CV, MAGE), HbA1c, hospitalization or emergency room visits for hypoglycemia or diabetes ketoacidosis.

We will collect baseline demographics, and available laboratory data (HbA1c, glucose, creatinine/BUN, hemoglobin, and hematocrit), current medications and Kt/V (dialysis adequacy test) from the electronic medical record, following HIPAA rules.

Subjects will be instructed to perform self-monitored blood glucose four times daily (4 point-SMBG) at home during the study duration (10 days), and to complete a DM diary (diabetic medications, food record). Compliance with SMBG will be quantified.

7.2 SAFETY AND OTHER ASSESSMENTS

Screening:

- **Anthropometric measures**
- **Vital signs** (e.g., temperature, pulse, respirations, blood pressure).

Follow-up

- **Assessment of study intervention adherence** or see Study Intervention Compliance, section 6.4 At least 70% of data (7days) after insertion of CGM
- **Administration of food record** (3 days), one (1) on a pre-dialysis day and one (1) on a dialysis day
- **Assessment of adverse events.** Describe provisions for follow-up of ongoing AEs/SAEs.

7.3 ADVERSE EVENTS AND SERIOUS ADVERSE EVENTS

7.3.1 DEFINITION OF ADVERSE EVENTS (AE)

Adverse event means any untoward medical occurrence associated with the use of an intervention in humans, whether considered intervention related.

7.3.2 DEFINITION OF SERIOUS ADVERSE EVENTS (SAE)

An adverse event (AE) or suspected adverse reaction is considered “serious” if, in the view of either the investigator or sponsor, it results in any of the following outcomes: death, a life-threatening adverse event, inpatient hospitalization or prolongation of existing hospitalization, a persistent or significant incapacity or substantial disruption of the ability to conduct normal life functions, or a congenital anomaly/birth defect. Important medical events that may not result in death, be life-threatening, or require hospitalization may be considered serious when, based upon appropriate medical judgment, they may jeopardize the participant and may require medical or surgical intervention to prevent one of the outcomes listed in this definition.

7.3.3 CLASSIFICATION OF AN ADVERSE EVENT

7.3.3.1 SEVERITY OF EVENT

- **Mild** – Events require minimal or no treatment and do not interfere with the participant’s daily activities.
- **Moderate** – Events result in a low level of inconvenience or concern with the therapeutic measures. Moderate events may cause some interference with functioning.
- **Severe** – Events interrupt a participant’s usual daily activity and may require systemic drug therapy or other treatment. Severe events are usually potentially life-threatening or incapacitating. Of note, the term “severe” does not necessarily equate to “serious”.]

7.3.3.2 RELATIONSHIP TO STUDY INTERVENTION

All adverse events (AEs) must have their relationship to study intervention assessed by the clinician who examines and evaluates the participant based on temporal relationship and his/her clinical judgment. The degree of certainty about causality will be graded using the categories below.

- **Probably Related** – There is clear evidence to suggest a causal relationship, and other possible contributing factors can be ruled out. The clinical event, including an abnormal laboratory test result, occurs in a plausible time relationship to study intervention administration and cannot be explained by concurrent disease or other drugs or chemicals. The response to withdrawal of the study intervention (de-challenge) should be clinically plausible. The event must be pharmacologically or phenomenologically definitive, with use of a satisfactory re-challenge procedure if necessary.
- **Possibly Related** – There is evidence to suggest a causal relationship, and the influence of other factors is unlikely. The clinical event, including an abnormal laboratory test result, occurs within a reasonable time after administration of the study intervention, is unlikely to be attributed to concurrent disease or other drugs or chemicals, and follows a clinically reasonable response on withdrawal (de-challenge). Re-challenge information is not required to fulfill this definition.
- **Potentially Related** – There is some evidence to suggest a causal relationship (e.g., the event occurred within a reasonable time after administration of the trial medication). However, other factors may have contributed to the event (e.g., the participant’s clinical condition, other concomitant events). Although an AE may rate only as “possibly related” soon after discovery, it can be flagged as requiring more information and later be upgraded to “probably related” or “definitely related”, as appropriate.
- **Unlikely to be related** – A clinical event, including an abnormal laboratory test result, whose temporal relationship to study intervention administration makes a causal

relationship improbable (e.g., the event did not occur within a reasonable time after administration of the study intervention) and in which other drugs or chemicals or underlying disease provides plausible explanations (e.g., the participant's clinical condition, other concomitant treatments).

- **Not Related** – The AE is completely independent of study intervention administration, and/or evidence exists that the event is definitely related to another etiology. There must be an alternative, definitive etiology documented by the clinician.

Relationship of AE to the Test Device:

Probable: Good reasons and sufficient documentation to assume causal relationship

Possible: Causal relationship is likely and cannot be excluded

Unlikely: The event is most likely related to an etiology other than the trial treatment

Unknown: Unable to assess due to insufficient evidence, conflicting data or poor documentation.

Anticipated Adverse Events (AAE) are considered to be those known, in terms of nature, severity and frequency, to be associated with the use of the test materials.

Unanticipated Adverse Events (UAE) are defined as any adverse experience that is not identified in nature, severity or frequency in the general investigational plan or elsewhere in the current application.

7.3.3.3 EXPECTEDNESS

Anticipated Adverse Events (AAE) are considered to be those known, in terms of nature, severity and frequency, to be associated with the use of the test materials.

The following events have been identified as possible device-related adverse events of **sensor insertion and wear**:

- Excessive pain or discomfort from either system deployment or during wear period (8 or greater on a 10-point Likert scale)
- Excessive bleeding, defined as requires removal of the device to stop bleeding
- Hematoma, defined as induration at the sensor insertion location (ecchymosis is a known consequence of needle skin puncture or pressure from sensor pod and will not be captured as an AE)
- Edema from sensor and/or adhesive tape that is significant and non-resolving within 48 hours of sensor pod removal
- Erythema from sensor and/or adhesive tape that is significant and non-resolving within 48 hours of sensor pod removal
- Local infection, defined as presence of pus at either sensor wire or sensor pod site
- Sensor or introducer needle fracture during insertion/wear/removal

Information regarding device-related AEs that occur during the study will be entered into appropriate CRFs. Such information will include, at a minimum:

- Date of event
- Severity
- Outcome
- Resolution of event

PI will be responsible for determining whether an adverse event (AE) is expected or unexpected. An AE will be considered unexpected if the nature, severity, or frequency of the event is not consistent with the risk information previously described for the study intervention.

TIME PERIOD AND FREQUENCY FOR EVENT ASSESSMENT AND FOLLOW-UP

The occurrence of an adverse event (AE) or serious adverse event (SAE) may come to the attention of study personnel during study visits and interviews of a study participant presenting for medical care, or upon review by a study monitor.

All AEs including local and systemic reactions not meeting the criteria for SAEs will be captured on the appropriate case report form (CRF). Information to be collected includes event description, time of onset, clinician's assessment of severity, relationship to study product (assessed only by those with the training and authority to make a diagnosis), and time of resolution/stabilization of the event. All AEs occurring while on study must be documented appropriately regardless of relationship. All AEs will be followed to adequate resolution.

Any medical condition that is present at the time that the participant is screened will be considered as baseline and not reported as an AE. However, if the study participant's condition deteriorates at any time during the study, it will be recorded as an AE.

Changes in the severity of an AE will be documented to allow an assessment of the duration of the event at each level of severity to be performed. AEs characterized as intermittent require documentation of onset and duration of each episode.

PI will record all reportable events with start dates occurring any time after informed consent is obtained until 15 (for non-serious AEs) or 30 days (for SAEs) after the last day of study participation. At each study visit, the investigator will inquire about the occurrence of AE/SAEs since the last visit. Events will be followed for outcome information until resolution or stabilization.

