2.3 RISK/BENEFIT ASSESSMENT

2.3.1 KNOWN POTENTIAL RISKS

1.a. Patients who develop hypoglycemia: We anticipate that ~50% of individuals recruited for this study will develop hypoglycemia by POC BG (as available).

During the observation study, blinded CGM data will be collected. Thus, subjects will be instructed to perform POC BG, as standard of care, for glucose monitoring. The study team will provide subjects with training on hypoglycemia management and prevention. If the study subject experiences hypoglycemic symptoms during the dialysis/blood glucose testing, we will notify the dialysis team to check a blood glucose and treat per standard of care. If POC BG or -YSI glucose is < 70 mg/dl, subjects will be given corrective measures, per standard of care, and communicate to their treating physician regarding subject's insulin doses and the need for follow-up for treatment of diabetes.

During the interventional study, all subjects will receive standard guidelines on how to adjust insulin based on CGM or POC BG data, and how to treat hypoglycemia per standard of care. The sensors provide a predictive hypoglycemia alarm ("predictive urgent low soon") that will alarm the subject within the preceding 20 minutes of a glucose < 55 mg/dl. The main objective of our RCT is to prevent hypoglycemia.

1.b. Risk of hyperglycemia.

We will exclude subjects with severe hyperglycemia (BG > 400 mg/dl) during consent/randomization. These subjects will be notified of the findings and advise to communicate with their treating physician for treatment adjustments.

1.c. Phlebotomy: Risks associated with phlebotomy and IV insertion are low and include small amounts of pain, possible bruising, swelling, redness, and rarely an infection at the site. However, we will collect blood from the pre-dialysis circuit and after the dialysis nurse inserted the dialysis needle. Approximately, ~5-10 ml of blood will be obtained during the dialysis for glucose testing (Aim 1b). These risks will be shared with the participants during informed consent and before starting the studies.

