Wash-Out Period (week 4-6): After completion of phase 1, all subjects will return to the clinic to remove the CGM and review the POC BG diary. After sensor removal, transmitter will be connected to the computer for data downloading. Sensor will be stored following standard precautions. Study personnel will input required clinical and demographic data into the sensor database software. During this period, no CGM will be worn, and all subjects will be reminded to perform self-monitored BG (SMBG) as usual.

Phase 2 (week 7-10): After completing the wash-out period, subjects initially randomized to the “Usual Care, Phase 1” arm will have a personal/real-time CGM inserted during the visit, and will be trained on how to use CGM to improve glycemic control (as described above) Subjects initially randomized to “Intervention Group, Phase 1” will then cross-over to the “Usual Care Group, and a blinded CGM will be used for up to 4 weeks.

Last Visit (week 10): After completing the 4 weeks’ assignment, subject will come back for CGM removal, if applicable. After sensor removal, transmitter will be connected to the computer for data downloading. Sensor will be stored following standard precautions. Study personnel will input required clinical and demographic data into the sensor database software

Guidelines to improve glycemic control using real-time CGM or POC BG:

Glucose Target	Know your personal glucose targets and take actions to reach them. My pre-meal target is 80 - 180 mg/dl . My post-meal target is < 200 mg/dl (2 hours after the start of a meal).
Low Glucose (Hypoglycemia)	Plan to prevent or to respond to hypoglycemia. Check POC glucose for confirmation. Eat 15 grams of carbohydrates (4 ounces of apple juice, or 4 glucose tablets) and repeat a fingerstick blood glucose measurement 15 minutes later. Repeat treatment if glucose <100 mg/dl every 15 min until BG > 100 mg/dl. Do not inject until glucose > 100 mg/dl.
CGM - Risk of Hypoglycemia (Urgent Low Soon Alarm)	For the “Urgent Low Soon Alarm” (predictive of hypoglycemia <55 mg/dL, within the preceding 20 minutes): 1) Eat 15 grams of carbohydrates and recheck in 15 minutes, 2) avoid injecting insulin or taking anti-diabetic agents until glucose is higher than 100 mg/dL, 3) check POC glucose for confirmation, 4) collect data in the diary.

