9.1.6 SAFETY OVERSIGHT

Safety oversight will be under the direction of a Data and Safety Monitoring Board (DSMB) composed of individuals with the appropriate expertise, including diabetes management, chronic kidney disease and diabetes devices. Members of the DSMB should be independent from the study conduct and free of conflict of interest, or measures should be in place to minimize perceived conflict of interest. The DSMB will meet at least semiannually to assess safety and efficacy data on each arm of the study. The DSMB will operate under the rules of an approved charter that will be written and reviewed at the organizational meeting of the DSMB. At this time, each data element that the DSMB needs to assess will be clearly defined.

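### Hypoglycaemia has no AE recording rule, and lows are noticed more completely on real-time CGM than under the blinded sensor, so hypoglycaemia AE counts are not comparable between phases and tend to count against the intervention

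*Combined protocol and SAP*

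**What the plan says.** All references are to the combined protocol and SAP, by the section numbers in the body.

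**What counts as an AE.** Section 7.3.1: "Adverse event means any untoward medical occurrence associated with the use of an intervention in humans, whether considered intervention related". The time-period text under Section 7.3.3.3 adds "All AEs occurring while on study must be documented appropriately regardless of relationship" and, for recurring events, "AEs characterized as intermittent require documentation of onset and duration of each episode".

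**What is left out.** The one event exempted by name is bruising at the sensor site: "ecchymosis is a known consequence of needle skin puncture or pressure from sensor pod and will not be captured as an AE". A general rule says that a condition already present at screening "will be considered as baseline and not reported as an AE", unless it deteriorates. No text says how either rule applies to low glucose. Yet hypoglycaemia is the first risk listed in Section 2.3.1: "We anticipate that ~50% of individuals recruited for this study will develop hypoglycemia by POC BG".

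**How AEs are found.** They come from study visits, interviews and monitor review, with an inquiry at each visit (7.3.3.3). In Aim 2 the Schedule of Activities places this at V2 to V5.

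**What the participant can see.** The real-time phase shows values, trends and alarms. The control phase uses a blinded sensor while the usual capillary checks continue (4.1). For the Urgent Low Soon alarm, the guideline table in Section 5.6.1 includes "3) check POC glucose for confirmation, 4) collect data in the diary". Section 2.2 says that finger-stick monitoring misses asymptomatic and nocturnal lows. Section 5.8 makes the trial open label but keeps investigators masked to the CGM data until all phases are complete.

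**Where the counts go.** Section 9.1.6: "The DSMB will meet at least semiannually to assess safety and efficacy data on each arm of the study". Section 7.3.5 asks for summaries of AE frequency and a periodic report of AEs above 5%. Section 6.1 puts all safety data in the study report.

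**The concern.** AE capture rests largely on what the participant noticed, and the intervention changes what the participant notices. The same low can be seen, confirmed and reported in one phase and pass unrecorded in the other. The alarm exists only in the real-time phase and itself prompts a finger-stick and a diary entry. So the imbalance would remain even if staff accepted only finger-stick-confirmed lows. Because investigators are masked to the sensor data, silent control-phase lows cannot be added to the AE record while the trial runs.

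At stake is how the safety data are read. In a trial whose question is hypoglycaemia prevention, the AE table could show more hypoglycaemia on real-time CGM while the sensor outcome shows less. The DSMB and later readers would have no stated basis for discounting the AE table.

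**Working it through.** The documents give no hypoglycaemia AE rate, so there is no planned figure to reproduce. The check asks how far recorded counts would depart from true counts.

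**Formula.** Recorded ratio (real-time : control) = true ratio × p_int / p_ctrl, where p is the share of episodes that reach the AE record. For the control phase, p_ctrl = s + (1 − s) × k × D / 1440.

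**Inputs**
- k = 4 evenly spaced finger-sticks a day. Sections 5.6.1 and 7.1 give four a day for the 10-day period; for the control phase the text says only that regular checks continue.
- D = episode length, 15 to 120 minutes (assumption).
- s = share of episodes noticed through symptoms and always reported: 0, 0.25 or 0.5 (assumption).
- p_int = 0.7 to 1.0 (assumption).

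**If the true rates are equal (true ratio 1)**

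| s | p_ctrl, D = 15 to 120 min | Lowest ratio (p_int 0.7, D 120) | Highest ratio (p_int 1.0, D 15) |
|---|---|---|---|
| 0.5 | 0.521 to 0.667 | 0.7/0.667 = 1.05 | 1/0.521 = 1.9 |
| 0.25 | 0.281 to 0.500 | 0.7/0.500 = 1.4 | 1/0.281 = 3.6 |
| 0 | 0.042 to 0.333 | 0.7/0.333 = 2.1 | 1/0.042 = 24 |

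The ratio exceeds 1 throughout. With one finger-stick a day and s = 0.5, p_ctrl is 0.505 to 0.542 and the ratio runs from 0.7/0.542 = 1.3 to 1/0.505 = 2.0, so less testing widens the gap.

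**If real-time CGM truly cuts episodes by 30%.** Here the four finger-sticks fall at random times, so a silent low of d hours is caught with probability 1 − (1 − d/24)^4. That is 0.157 for 1 hour and 0.294 for 2 hours. With half of episodes symptomatic, p_ctrl = 0.5 + 0.5 × 0.157 = 0.578 and 0.5 + 0.5 × 0.294 = 0.647.

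| | 1-hour lows | 2-hour lows |
|---|---|---|
| Recorded ratio, p_int = 1 | 0.70/0.578 = 1.21 | 0.70/0.647 = 1.08 |
| Recorded ratio, p_int = 0.7 | 0.49/0.578 = 0.85 | 0.49/0.647 = 0.76 |
| p_int at which recorded counts are equal | 0.578/0.70 = 0.83 | 0.647/0.70 = 0.92 |

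So in the half-symptomatic case a true 30% reduction is recorded as an increase only if capture on real-time CGM exceeds about 83% (1-hour lows) or 92% (2-hour lows). If all lows are silent, it is recorded as an increase even at p_int = 0.7 (0.49/0.157 = 3.1; 0.49/0.294 = 1.7).

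**The case against.** **Control-phase lows are not invisible.** A reader might infer that participants learn of lows only on real-time CGM. The documents do not support that. Capillary checks continue, self-monitoring results are collected at V3, V4 and V5, and about half of participants are expected to show hypoglycaemia by finger-stick. What stands is a difference in completeness, mainly for asymptomatic, nocturnal and between-test lows.

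**No text says that each low is an AE.** A reader might infer that each must be logged. That is an inference: there is no glucose threshold, hypoglycaemia is absent from the anticipated-event and special-interest lists, and the bruising exemption only clarifies an item in a device-site list. Recurrent lows might also be baseline, since prior hypoglycaemia is a randomisation factor. This stands, but it leaves the matter to individual judgement in an open-label trial, which is a reason to write the rule.

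**The diary step is narrower than it looks.** It belongs to a predictive alarm, and a diary entry is not an AE report. Diaries are also issued for both phases. True, but the alarm-prompted finger-stick and entry still occur only in the real-time phase and give the participant more to report.

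**Nothing formal depends on these counts.** Section 8 plans no test of them, the statistical stopping rule concerns death, and the DSMB sees efficacy data as well. Its charter, which is to define its data elements, is not among the documents and may deal with this. This limits the consequence to misreading of descriptive tables; it does not make the counts comparable.

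**Conclusion.** The point holds as one of differential ascertainment. Under the stated capture rules, hypoglycaemia AE counts set side by side by phase are not comparable and tend to be biased against real-time CGM. The direction holds across the range examined. The size rests on assumptions outside the documents: with equal true rates, about 1.1 to 1.9 if half of episodes are symptomatic, about 1.4 to 3.6 if a quarter are, and larger still if all are silent. The direction would fail only if capture on real-time CGM fell below control-phase capture, for instance through poor recall at visits weeks apart.

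A reader might conclude that a real benefit would be recorded as harm. That is not established: the net recorded difference could go either way, depending on the true effect and on capture. Nor does the point touch the primary outcome or the other CGM-measured outcomes, which use sensor data in both phases. Hospitalisation and emergency visits do not depend on seeing the display in the same way.

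I have read arm in Section 9.1.6 as treatment phase. If it means sequence group, each group contributes both phases and the bias would largely cancel in totals over completed participants. It would return in any tabulation by phase.

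The change should be made; confidence is medium.

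**What to change.** Add to Section 7.3, for Aim 2:

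1. Between-phase hypoglycaemia counts for the DSMB and the study report come from the downloaded sensor record of both phases, using one algorithm fixed in advance. Someone outside the masked team prepares them, so that Section 5.8 still holds.
2. A glucose value alone is not entered as an AE.
3. Hypoglycaemia AEs and SAEs are compared by phase only on criteria that can be observed equally in both: help from another person, emergency visit, hospitalisation, or otherwise meeting the SAE definition. The same question is asked at V3 and V5.
4. Any other self-noticed lows that are recorded are listed and labelled as not comparable between phases.

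The same text should say how the baseline-condition rule applies to recurrent hypoglycaemia. SAE reporting and the participant guidelines on responding to glucose values and alarms stay as they are.

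**Cost.** Protocol and CRF wording and one derived sensor table; the sensor data are already downloaded in both phases. The downside is that mild self-treated lows leave the comparative AE table, though they remain in the sensor-based one.
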